**[name]1†(PhD), [name]2†(PhD), [name](PhD), [name]**

**[name](PhD)**

**Study protocol**

**Ethical committee approval date:10/1/2021**

## Introduction

Burn is one of the most devastating injuries that have a catastrophic effect on people in terms of human life, suffering, disability, and financial loss. Burns are the third leading cause of accidental death in the United States; approximately 5000 people die each year from burns. Each year an estimated 2 million Americans experience burns severe enough to seek medical care .

In Egypt, minimal studies discussed epidemiological records of burn, however it has been reported that burn cases were around 100.000 in 2018. Statistical records of the Burn Unit at the Main University Hospital; Alexandria, revealed that; 314 burn cases were admitted to unit in 2020 .

Burns are caused by transfer of energy from a heat source to the body; which may be transferred through conduction or electromagnetic radiation. The depth of the injury depends on the temperature of the burning agent and the duration of contact with that agent. Burns are categorized as thermal (which include electrical burns), radiation, or chemical, in which tissue destruction results from coagulation, protein denaturation, or ionization of cellular contents. 

Wound healing is a complex process, involves optimizing patient local and systemic conditions in conjunction with an ideal wound healing environment. Many different products have been developed to influence this wound environment to provide a pathogen-free, protected, and moist area for healing to occur. Newer products are currently being used to replace or augment various substrates in the wound healing cascade; such as Silver, Negative Pressure Wound Devices, Skin Substitutes, Growth Factors and Biologic Wound Products, Hyperbaric Oxygen, and herbal therapy .

Burn hospital wound's protocols vary, but the most common wound cleaning involves saline and povidone-iodine (Betadine). Wound is cleansed at each dressing change and is observed for signs of infection and rate of healing. This may be done in the hydrotherapy tub, shower, or at bedside .

Recent studies showed that alternative therapies are used as first aid treatment for burns as Aloe Vera, saliva and a tea tree oil impregnated dressing applied as first aid to a porcine deep dermal contact burn, results of it showed significantly decrease sub dermal temperature within the skin during the treatment period.

Tea tree oil [TTO] (*Melaleuca alternifolia*) is a clear, colorless to pale yellow liquid, and is insoluble in water. It is lipophilic and works through penetrating the skin and mucous membranes. The active ingredients responsible for killing bacteria and fungi in TTO include terpinene-4-ol, alpha-terpineol and alphaphinene, which inhibit cell respiration and disruption of cell membrane permeability with the resultant leakage of potassium.

Inherent in the previous statements, is the belief that there is a need to investigate whether TTO would be more cost effective, enhance rapid healing than the conventional topical agent.

### **Aim of the study**

Compare the effect of two topical dressing techniques on the healing of second degree burn wounds; *melaleuca alternifolia* (tea tree oil) and conventional dressings.

### **Operational definition**

#### **Conventional dressing:**

Sterile topical gauze dressing are impregnated with or laid over a topical antibiotic, silver sulphadiazine with adhesive tape to secure dressing.

### **Materials and method**

#### **Materials**

**Design:** An experimental design will be utilized.

**Setting:** The present study will be conducted at the burn unit, Alexandria Main University Hospital, Alexandria, Egypt.

**Subject:** A convenient sample of 50 patients admitted to burn unit suffering from second-degree burns will be included in the present study.

The fifty patients will be sequentially enrolled into two equal groups:-

- The first group (25 patients) will be managed conventional dressings (control group).

- The second group (25 patients) will be managed by local application tea tree oil (study group).

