**Patient's inclusion criteria will include:**

- Adults of both genders (18-60 years), able and willing to cooperate and communicate.
- Newly admitted to the study setting with recent 2nd degree burns whether superficial or deep ≤10%TSBA.
- Free of associated illness that affect wound healing as DM, immune disorder, or associated injuries.
- Free from pre-existing skin conditions such as eczema

**Tools:** Two tools will be used on this study:

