## **Method**

1. Written approval will be obtained from the hospital administrator and head of Burn Department, after explanation of the study aim.
2. The study tools will be developed by the researcher after review of relevant literature.
3. The developed tools will be submitted to 5 experts in the fields of plastic surgery &burn and Medical Surgical Nursing to test its content validity and necessary modification will be done accordingly.
4. Reliability of the tool will be tested.
5. Ethical considerations:
  - a. Patient's written informed consent will be obtained after explanation of the study aim.
  - b. Confidentiality, privacy and right of withdrawal will be assured.
  - c. Ethical committee approval will be obtained.
6. Pilot study will be conducted on 5 patients for testing, clarity, feasibility and applicability of the developed tools and modification will be done.
7. The study subjects meeting inclusion criteria and will be sequentially divided into two groups, the first group will receive conventional dressing (control group), and this dressing will be changed routinely once every other day. For the second group the wound will be dressed by TTO, which will be changed every other day till healing occurs. This frequency is advocated, since more frequent dressing change will interfere with granulation tissue formation.
8. All burn wound will be washed gently with Saline, and all open blister and loose non-viable tissue will be removed from the burn, intact blisters will be

left, and then the topical agents will be applied directly on wound. Burns involving body joints will be kept in functional position.

9. Initial assessment of all patients will be done using tool I. Subsequent assessment will be done on 4th, 14th, 21th of topical dressing agents use until the wound healing from both groups using tool II.
10. Colored digital photographs will be taken-if possible- to assess wound healing process at the (day of burn, each other day till healing, after one month)
11. Initial and ongoing assessment results for the conventional dressing, compared to TTO dressings, will be carried out using appropriate statistical methods.

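### The 50 patients are a convenience sample with no requirement to approach or record every eligible admission, which limits who the result describes and, with predictable assignment, could make the groups differ

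*Combined protocol and SAP*

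**What the plan says.** The only statement of how the 50 patients are obtained is under Materials (Subject): "A convenient sample of 50 patients admitted to burn unit suffering from second-degree burns will be included in the present study". The next sentence concerns the groups: "The fifty patients will be sequentially enrolled into two equal groups". Method, item 7, repeats the idea: "The study subjects meeting inclusion criteria and will be sequentially divided into two groups". The groups have 25 patients each, the first on conventional dressing and the second on tea tree oil.

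Eligibility is broad in severity ("Newly admitted to the study setting with recent 2 nd degree burns whether superficial or deep ≤10%TSBA") and includes one criterion that needs judgement ("Adults of both genders (18-60 years), able and willing to cooperate and communicate"). The Introduction gives one figure on patient flow: "314 burn cases were admitted to unit in 2020". Tool I records depth, extent, site and cause of the burn and the date of admission.

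The document has no screening log, no count of eligible or declining patients, no stated recruitment period, and no description of randomisation or concealment. The Statistical Analysis Plan compares the groups with unadjusted tests and does not stratify by burn depth or extent.

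**The concern.** A convenience sample leaves open which eligible patients are taken, and the plan keeps no trace of the others. Two things are at stake.

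The first is whom the result describes. The aim refers to second-degree burns in general, and eligibility runs from superficial to deep. If milder or easier burns are more likely to enter, the result describes those burns, and a reader has no denominator against which to judge it.

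The second is the comparison itself. Sequential assignment may mean alternation, or the first 25 patients to control and the next 25 to tea tree oil. On either reading, whoever enrols can know the next patient's group. Discretion over entry can then act differently in the two groups, and the unadjusted tests would carry the imbalance into the result.

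**Working it through.** **Reading the passages together.** The phrase about a convenience sample governs how the 50 are found. In both places where the word for sequential appears, it governs how patients are placed into two groups. Neither sentence says that admissions are taken in order or that none may be passed over, and neither rules out entry in order of admission. The text leaves the order of entry unsettled.

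**The plan's own figure.** The document gives no calculation for N = 50, so there is nothing to reproduce. The point does not depend on one: consecutive entry leaves N at 50 (25 per group) and power unchanged.

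**Feasibility of consecutive entry.** Inputs are N = 50 (Materials) and 314 admissions a year (Introduction, all burns). The eligible share *f* is not given, so it is assumed.

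Months to accrue = 50 / (314 × *f* / 12), if every eligible patient enters.

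| Assumed *f* | Eligible per year | Months for 50 |
|---|---|---|
| 10% | 31.4 | 19.1 |
| 25% | 78.5 | 7.6 |
| 50% | 157 | 3.8 |

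Since 50 / 314 = 15.9%, an eligible share below about 16% would mean that 50 patients exceed a full year's supply. The number of eligible patients who might be passed over therefore cannot be inferred from the document.

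**How selection could act (illustration only).** Assume that prognosis is standard normal, groups alternate, and a share *q* of below-average patients is passed over. The mean prognosis of those accepted is

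0.399 × *q* / (1 − *q*/2),

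where 0.399 is the standard normal density at zero.

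- *q* = 0.1: 0.0399 / 0.95 = 0.04 SD
- *q* = 0.3: 0.1197 / 0.85 = 0.14 SD
- *q* = 0.5: 0.1995 / 0.75 = 0.27 SD

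A simulation of 4,000 trials per setting agrees:

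| *q* | Selection ignores next group: shift of whole sample | Same: group difference | Selection only when tea tree oil is next: group difference |
|---|---|---|---|
| 0.1 | 0.04 SD | about 0 | 0.04 SD |
| 0.3 | 0.14 SD | about 0 | 0.15 SD |
| 0.5 | 0.26 SD | about 0 | 0.26 SD |

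There is no treatment effect in this model, and taking every patient brings both quantities to about 0. The values of *q* have no source in the document. What the table shows is the mechanism: selection alone shifts who is described, and it biases the comparison only when it is linked to the known next group.

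**The case against.** The strongest reply is that this concerns generalisability, that many trials recruit this way, and that the real weakness is the allocation. Much of that stands. When selection is unrelated to the next group, the group difference in the illustration stays at about zero. Non-random, unconcealed allocation is the more serious defect.

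Several stronger readings are tempting and are not supported:

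- *That staff pick the patients they prefer.* The document does not say who selects, and explicit criteria confine any discretion to eligible patients.
- *That patients are definitely not taken in order.* Sequential enrolment could be meant that way, and a convenience sample at one unit can be consecutive.
- *That the case mix cannot be checked.* Tool I will show the depth and extent of the burns enrolled. What is missing is the corresponding information on eligible patients who were not enrolled.
- *That 314 admissions a year prove many eligible patients will be passed over, or that consecutive entry is easy.* The figure counts all burn cases, without the study's limits on age, depth, extent or associated illness. At 10% eligible there may be none to spare in a year.
- *That consecutive enrolment cures the problem.* Consent and the cooperation criterion still leave some discretion, and admissions can be missed when no research staff are present.

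What the reply does not remove is that the stated sampling rule permits selection among eligible patients, nothing records it, and the assignment method gives it a route into the comparison.

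**Conclusion.** The point holds as a minor one. The plan states a convenience sample, does not require every eligible admission to be approached or recorded, and leaves the order of entry unclear. This limits whom the result describes. Combined with predictable, unconcealed assignment, it could also make the groups differ.

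No magnitude can be derived from the document, since the eligible share, the recruitment period and the way patients are approached are not given. The accrual range of about 19 to 4 months rests on the assumed 10% to 50% eligible, and the SD shifts are illustrative. The document does not show that selection would take place, only that the plan neither prevents nor reveals it.

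**What to change.** 1. Under Materials (Subject), replace the convenience-sample wording with: *the first 50 consecutive admissions that meet the criteria and consent*.
2. Reconcile this with the sentence on sequential enrolment, and with Method item 7, by stating separately how patients enter the study and how they are placed in a group.
3. Keep a screening log with one line for each second-degree burn admission: date, depth, extent, eligible yes/no, and reason not enrolled. Log admissions missed for want of research staff as missed, so that departures from consecutive entry can be counted.
4. Report the counts.

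The cost is a change of protocol wording and a little clerical time, with N and power unchanged. The log should start before enrolment, because it cannot be rebuilt reliably afterwards.

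These steps reduce selection and make it visible. They do not replace concealed random allocation, do not stop consent from differing by known group, and do not remove calendar-time confounding if the first 25 patients are all controls.

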**Patient's inclusion criteria will include:**

- Adults of both genders (18-60 years), able and willing to cooperate and communicate.
- Newly admitted to the study setting with recent 2nd degree burns whether superficial or deep ≤10%TSBA.
- Free of associated illness that affect wound healing as DM, immune disorder, or associated injuries.
- Free from pre-existing skin conditions such as eczema

**Tools:** Two tools will be used on this study:

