**Tool I: (Burn patient's assessment sheet)**

This tool will mainly aim to assess burn parameters (as extent, depth, and cause of burn), criteria of wound healing (as wound color, appearance of burn wound, signs of infection and presence of exudates). It will be comprised of three parts.

**Part I: Patient Sociodemographic data:** including:

- Personal characteristics: as Patients' age, gender, level of education, occupation, date of burn, date of admission, date of discharge and habits.
- Patient history including past and present history.

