**-Morphological changes of the wound:**

This part will be used to assess burn wound healing, and determine signs of infection including signs of inflammation as wound color, presence of exudates (amount, color, and type), size, depth, edema, as well as frequency of dressing change.

- **Photographic pictures:**

Colored digital photographs will be taken three times to assess wound healing process (day of burn, each other day till healing and after one month)

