#### **Statistical Analysis Plan (SAP):**

Data will be analyzed using IBM SPSS software package version 23.0. The Shapiro-Wilk will be used to verify the normality of distribution of variables; Comparisons between groups for categorical variables will be assessed using Chi-square test (Monte Carlo or Fisher Exact). Student t-test will be used to compare two groups for normally distributed quantitative variables, Mann Whitney test will be used to compare two groups for not normally distributed quantitative variables, Friedman Test for multiple comparisons between the different periods in each group. Significance of the obtained results will be judged at the 0.5% level.

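### Tool II visits are counted from first dressing and entry has no limit on burn age, yet the analysis ignores time since burn, adding noise and leaving any wound-age difference between arms uncorrected

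*Combined protocol and SAP*

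**What the plan says.** **Entry.** The inclusion criteria ask for a patient "Newly admitted to the study setting with recent 2 nd degree burns whether superficial or deep". No maximum number of hours or days since injury is given anywhere.

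**Visit clock.** Method item 9 states: "Subsequent assessment will be done on 4 th , 14 th , 21 th of topical dressing agents use". Day 0 is thus the start of the study dressing.

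**Photograph clock.** Method item 10 states: "Colored digital photographs will be taken-if possible- to assess wound healing process at the (day of burn, each other day till healing, after one month". The photographic part of Tool II also begins on the day of burn.

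**Dates collected.** Tool I, Part I lists "date of burn, date of admission, date of discharge and habits". The date of the first study dressing is not named.

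**Allocation.** Under Materials: "The fifty patients will be sequentially enrolled into two equal groups". Method item 7 repeats the sequential division. Neither describes randomisation or stratification.

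**Analysis.** The SAP says "Student t-test will be used to compare two groups for normally distributed quantitative variables", with Mann-Whitney and chi-square tests as the alternatives and Friedman tests within each group. No covariate is named, and time since burn does not appear.

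**The concern.** A wound starts to heal at injury, not at the first study dressing. A patient dressed on the day of the burn and one dressed some days later reach the same Tool II visit with wounds of different ages. Two consequences follow.

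1. Within each arm, variation in the delay from burn to first dressing adds variation to the healing outcome. With 25 patients per arm this costs precision.
2. If the average delay differs between arms, the arm with the older wounds looks faster at every Tool II visit even when the dressings are equivalent. Sequential allocation without randomisation does nothing to prevent this, and the planned tests would not correct it. The error could favour either dressing.

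At stake is the aim itself: to compare the two dressings on healing.

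**Working it through.** The documents give no healing-time SD, delay distribution, effect size or power, so there is no figure of the plan's own to reproduce. The only numerical inputs taken from the documents are 25 patients per arm (Materials) and the 0.5% significance level (SAP). The rest are assumptions, shown over a range. Days to healing serves as the illustrative outcome.

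**Step 1: noise from varying delay.** Let *h* be the SD of healing time counted from the burn and *d* the SD of the delay from burn to first dressing, with the two independent. Time counted from first dressing is healing time minus delay, so its variance is *h*² + *d*². The inflation is (*h*² + *d*²)/*h*², and the standard error grows by its square root.

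| Delay SD *d* (days) | *h* = 4 | *h* = 6 | *h* = 8 |
|---|---|---|---|
| 1 | 17/16 = 1.06 | 37/36 = 1.03 | 65/64 = 1.02 |
| 2 | 20/16 = 1.25 | 40/36 = 1.11 | 68/64 = 1.06 |
| 3 | 25/16 = 1.56 | 45/36 = 1.25 | 73/64 = 1.14 |

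For *d* = 2, a healing SD of 4 to 6 days gives 25% to 11% more variance. The standard error is √1.25 = 1.12 to √1.11 = 1.05 times as large, that is, 12% to 5% larger.

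**Step 2: what a systematic difference would do, if there were one.** Suppose the dressings are equivalent and one arm's wounds are on average Δ days older at first dressing. The standard error of the difference in means is *h*√(2/25), here leaving out the extra noise from step 1. The two-sided false-positive rate is Φ(Δ/SE − z) + Φ(−Δ/SE − z), with z = 1.96 at 5% and 2.81 at 0.5%. For *h* = 4 and Δ = 2, SE = 1.13 and Δ/SE = 1.77, so the 5% rate is Φ(−0.19) = 42%.

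| Δ (days) | Level | *h* = 4 | *h* = 6 | *h* = 8 |
|---|---|---|---|---|
| 0 | 5% | 5% | 5% | 5% |
| 1 | 5% | 14% | 9% | 7% |
| 2 | 5% | 42% | 22% | 14% |
| 2 | 0.5% (as written) | 15% | 5% | 3% |

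In terms of visits, assume a mean healing time of 18 days from burn, *h* = 6, and a mean delay of 1 day in one arm and 3 days in the other. The proportions healed by dressing day 14 are Φ((15 − 18)/6) = 31% and Φ((17 − 18)/6) = 43%. By day 21 they are Φ((22 − 18)/6) = 75% and Φ((24 − 18)/6) = 84%.

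These figures show how sensitive the comparison is. They do not estimate what will happen in this trial, because nothing in the documents indicates Δ. With Δ = 0 the rates return to nominal and only the noise of step 1 remains.

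**The case against.** Much can be said for the plan. Counting follow-up from the start of treatment is a normal choice. Requiring a new admission shortens the time from admission to dressing, and planning a photograph on the day of burn suggests that early enrolment was expected. The date of burn is collected, so wound age can be calculated later. Tool I's list may be illustrative, and item 9 visits cannot be scheduled without knowing when dressing began. On the smaller assumed SDs of delay, the noise is slight. All of this stands, and it makes the problem modest and easy to repair. It does not remove it: no entry rule bounds the time from burn to admission, and no planned analysis uses the date of burn.

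A reader might infer more than the documents support:

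- **That chance imbalance in wound age biases the result.** With 25 per arm and a delay SD of 1, 2 or 3 days, the difference in mean delay has a standard error of SD × √(2/25) = 0.28, 0.57 or 0.85 days. That is random error which the observed SD, and so the t-test, already reflects. It costs precision and does not raise the false-positive rate. Bias needs a systematic difference.
- **That such a bias has been shown.** It has not. Non-random allocation leaves it possible, no more.
- **That natural healing is credited to tea tree oil.** The aim compares two dressings. Natural healing occurs in both arms and cancels unless wound age differs between them.
- **That the two clocks corrupt the endpoint.** Photographs are taken only where possible, the SAP names no photographic endpoint, and after the first picture they follow the same every-other-day rhythm as the dressing changes. The conflict is essentially one baseline photograph. Whether any patient will enter too late to have it is unknown.

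**Conclusion.** The point holds as a recommended improvement. The certain part is a loss of precision whenever delays vary and wound state depends on time since burn: about 11% to 25% more variance for a delay SD of 2 days and a healing SD of 6 to 4 days, and between 2% and 56% over the wider assumed grid. The possible part is a systematic difference in wound age, which sequential allocation does not prevent and the unadjusted tests would report as a dressing effect. Its size cannot be computed from the documents, and the false-positive rates above apply only if the assumed 1- or 2-day difference exists. The lack of a definition for a recent burn is a secondary matter of clarity.

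**What to change.** 1. Add the date of the first study dressing to Tool I and make it the single day 0 for Tool II and photographs. Take the baseline photograph just before that dressing, so that every patient can have one.
2. Derive days from burn to first study dressing, report it by arm, and include it as a covariate in the healing comparison (for example, a linear model in place of the t-test, or a logistic model for healed by a given visit). The fitted slope lets the data show how far earlier days count towards healing.
3. As a sensitivity result, compare healing time counted from the burn date, without the covariate. In a linear model that already contains the delay, changing the origin leaves the dressing estimate unchanged, so an adjusted version would add nothing.
4. As a secondary clarification, the investigators should reconcile the undefined recency criterion with the planned day-of-burn photograph. Any limit is theirs to set before enrolment.

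Items 1 to 3 cost one extra date, one derived variable and one model term. They exclude no patient and change no treatment. Adjustment removes noise and the part of a between-arm wound-age difference that the covariate captures. It does not repair other imbalances that sequential allocation may bring.

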**Part II: Laboratory studies:**

- Complete blood count.
- Serum proteins.
- Electrolytes.

**Part III: Burn parameters:** This part will include data regarding: Site of burn, extent, cause, and depth.

**Part IV: Type of wound dressing:** Whether TTO or Conventional dressing.

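### Baseline burn depth and extent are recorded, but no between-group healing test adjusts for them; pre-specifying an adjusted comparison is a cheap improvement

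*Combined protocol and SAP*

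**What the plan says.** The inclusion criteria admit recent second-"degree burns whether superficial or deep ≤10%TSBA". Tool I is meant to "assess burn parameters (as extent, depth, and cause of burn", and its Part III repeats this: "This part will include data regarding: Site of burn, extent, cause, and depth". Method item 9 fixes the timing: "Initial assessment of all patients will be done using tool I". Depth and extent are therefore baseline values available for every patient.

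On allocation, the Subject paragraph says "The fifty patients will be sequentially enrolled into two equal groups". Neither it nor Method item 7 describes a chance mechanism or stratification by depth.

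The SAP lists chi-square (Monte Carlo or Fisher), Student t and Mann-Whitney tests between groups, and a Friedman test within each group, judged at the 0.5% level. None carries a covariate or stratum. Method item 11 plans to compare "Initial and ongoing assessment results for the conventional dressing, compared to TTO dressings", with the choice of method left open. Tool II records the wound again at follow-up, including "presence of exudates (amount, color, and type), size, depth, edema". No single main healing outcome is named.

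**The concern.** Superficial and deep burns may heal at different speeds. If they do, two things follow in an unadjusted test. The variation due to depth stays in the error term, so the test is less precise than the collected data allow. And if one arm receives more deep burns, the difference between arms mixes depth with dressing: it can look like a tea tree oil effect or hide one. Comparing baseline depth between groups, which item 11 permits, can reveal an imbalance but does not remove it from the healing result.

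Because depth is recorded again on Tool II, the plan also needs to say which value may be used. Follow-up depth can be affected by the dressing and is not a legitimate adjustment variable.

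**Working it through.** **From the documents:** 25 per arm; depth and extent at baseline; level 0.5% as written (taken as two-sided; 5% shown for comparison). There is no power, SD, healing time or effect size to reproduce.

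**Assumed:** the outcome is time to healing, since the Introduction asks whether tea tree oil would "enhance rapid healing than the conventional topical agent". Superficial mean in controls 13 days; SD 3 days (superficial) and 4 days (deep); half the burns deep; 3-day benefit; extent spread evenly over 1-10% with **no effect on healing**; an exact healing time for all 50 patients. The depth gap g (deep minus superficial mean) is varied. The comparison is a t-test against a linear model with treatment, depth and extent, in 20,000 simulated trials per case.

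**1. Precision, depth varying by chance.**
- Mean within-depth variance: (9 + 16)/2 = 12.5. Variance due to depth: 0.5 × 0.5 × g² = 0.25g².
- Unadjusted SE² = (2/25)(12.5 + 0.25g²) = 1.00 + 0.02g².
- Adjusted SE² ≈ (2/25)(12.5)(1 + 2/45) = 1.044, whatever g is; the factor 2/45 is the price of two covariates.
- The formulas give unadjusted SEs of 1.000, 1.039, 1.149 and 1.510 and an adjusted SE of 1.022. The simulation agrees:

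| Gap (days) | SE unadjusted | SE adjusted | Power at 5% | Power at 0.5% |
|---|---|---|---|---|
| 0 | 0.994 | 1.016 | 84% to 82% | 53% to 51% |
| 2 | 1.034 | 1.016 | 81% to 83% | 49% to 50% |
| 4 | 1.144 | 1.017 | 72% to 82% | 38% to 50% |
| 8 | 1.503 | 1.016 | 50% to 82% | 18% to 51% |

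Break-even: 0.02g² = 0.044, so g² = 2.2 and g is about 1.5 days.

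The 8-day row is the least secure. Deep control burns then average 13 + 8 = 21 days, so half heal after day 21, the last Tool II visit that is named by day.

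**2. Bias under imbalance.** With 17 deep burns in controls and 8 in the study arm, the unadjusted difference is shifted by (17 − 8)/25 × g = 0.36g, or 1.44 days at g = 4. With no true effect and g = 4, the chance of a significant result favouring tea tree oil is:
- 5% level: about 21% unadjusted, 2.5% adjusted (nominal 2.5%).
- 0.5% level: 3.7% unadjusted, 0.2% adjusted (nominal 0.25%).

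At 15 vs 10 deep the same case gives 7% unadjusted at the 5% level, and little change at 0.5%. With the imbalance reversed (8 deep in controls, 17 in the study arm) and a real 3-day benefit, power at 5% is 25% unadjusted and 77% adjusted.

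**3. How likely such splits are by chance.** Exact binomial, half deep: a difference of 5 or more deep burns has probability 20%; 9 or more (as in 17 vs 8), 1.5%.

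**4. Cost if neither variable predicts healing (g = 0).**

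| Deep burns | Power at 5% | Power at 0.5% |
|---|---|---|
| By chance | 84% to 82% | 53% to 51% |
| 17 vs 8 | 84% to 77% | 53% to 44% |
| 20 vs 5 | 84% to 64% | 53% to 29% |

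**The case against.** Unadjusted tests are not an error in themselves, and nearly every input above is assumed. That stands: at gaps of 0 to 2 days the change in power is within about 2 points either way. A reader might take the move from 50% to 82% as the expected gain. The documents do not support that, because they give no depth effect and that row depends on exact healing times beyond day 21.

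A reader might also infer that the arms will be imbalanced. The documents show only that no chance mechanism is described. That removes the bound which randomisation would give, but it does not predict a 17 vs 8 split.

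A third tempting reading is that the simulation justifies adjusting for extent. It does not: extent was given no effect, so here it could only cost precision. Including it is a judgement, reasonable because it is recorded and varies up to 10%.

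The plan's general wording (suitable statistical methods in Method item 11, suitable correlation and tests in Results) leaves room for adjustment. But it specifies none, and a choice made after seeing the data is what pre-specification is meant to prevent.

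Two practical objections stand and shape the fix. A linear model for time to healing has no place for wounds unhealed at last observation. And the SAP names SPSS 23.0 without any check that it runs the less common methods.

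**Conclusion.** The point holds as a recommended improvement, not as an error in the plan. The facts are plain: depth and extent are baseline data, and no planned between-group test uses them. The benefit depends on how strongly depth predicts healing. Under the assumptions above it runs from a loss of about 2 points to a gain of about 32 points at either level (50% to 82%, and 18% to 51%), with break-even near a 1.5-day gap; the top of that range is the weakest part. Protection against bias from a depth imbalance is the second benefit, and it matters more here because allocation is sequential.

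A reader might conclude that adjustment would make the groups comparable. It would not: it deals with measured depth and extent only, and cannot replace random allocation.

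**What to change.** Name one main healing outcome before analysis, and add to the SAP:

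> The main between-group healing comparison will be adjusted for baseline burn depth (superficial/deep) and extent (% body surface) from Tool I; unadjusted tests are supportive. Depth recorded at follow-up (Tool II) will not be used for adjustment.

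Then fix one method to match the outcome:
- **Wound size:** linear model with treatment, depth and extent.
- **Healed yes/no at a fixed visit:** penalised logistic model with the same terms.
- **Ordered category, such as exudate amount:** Mann-Whitney test stratified by depth (van Elteren), with the SAP sentence changed to say depth only.
- **Time to healing:** a method that treats wounds unhealed at last observation as censored, such as a log-rank test stratified by depth (again changing the sentence to depth only) or a Cox model with depth and extent. Use a linear model only if healing is observed for all patients.

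Confirm that the chosen method runs in the named software, or name other software. If depth turns out badly imbalanced, report adjusted and unadjusted results together and say that precision is reduced.

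The work is SAP wording and one model on data already collected: no new form, visit or patient. The statistical cost, if neither variable predicts healing, is about 2 power points with chance imbalance at either level; about 6-7 points (5%) or 9 points (0.5%) at 17 vs 8 deep; and about 20 or 23 points at 20 vs 5. If depth does matter, those same splits are where the unadjusted result is most biased.
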